Appendix 1 Time and Events Schedule

Single-dose Phase (Cohorts 1, 2, 3, and 4)	Screening ^a	Treatment						EOT ^b	EOS ^c
Day	-4 to Start of Treatment	1						2	28 (+ 7) Days After Dosing
Hour		0	1	3	3.5	5	8	24	
Administrative Procedures									
Informed consent/assent	X								
Inclusion/exclusion criteria	X								
Medical history	X								
Signs and symptoms	X							X	
Demographics & baseline characteristics	X								
Review of prior/concomitant medications	X ← → X								
Clinical Procedures									
Physical examination	X							X	
Vital sign measurements	X		X				X	X	
Mandatory clinical laboratory tests (see Table 7-3)	X							X	
eGFR ^e	X								
Pregnancy test ^f (urine)	X								
Adverse event monitoring	X ← → X								
Liver Event Form (if criteria in Appendix 2 are met)	X ← → X								
Study Treatments									
Administration of cefiderocol study drug ^g		X	→ X						
Pharmacokinetic Assessments									
Cohorts 1 and 2: Blood sample collection ^h			X	X	X	X	X		
Cohorts 3 and 4: Blood sample collection ⁱ				X		X	X		

eGFR = estimated glomerular filtration rate; EOS = End of Study; EOT = End of Treatment; IV = intravenous

- a Screening will occur within 4 days prior to Treatment Day 1 or on Treatment Day 1.
- b EOT assessment will occur within 24 hours after administration of study treatment or at early termination.
- c EOS visit will occur 28 (+ 7) days after administration of study treatment, on-site or via telephone call.
- d Body weight measurement only at Screening.
- e eGFR (based on Schwartz equation [10] if ≥ 3 months to < 1 year of age and modified Bedside Schwartz equation [11] if ≥ 1 to < 18 years of age) will be estimated at Screening and predose (if more than 24 hours after Screening). See [Section 7.5.3.1.2](#) for eGFR calculations and ranges.
- f Female subjects of childbearing potential only.
- g Cefiderocol administered as an IV infusion over 3 hours. Infusion time must be 3 hours in the single-dose phase, but may be shortened in the multiple-dose phase.
- h Cohorts 1 and 2: Blood samples will be collected: 1, 3 (within 15 minutes prior to the end of infusion using a separate line or immediately after the end of infusion using the same line and with proper flushing), 3.5, 5, and 8 hours after the start of infusion.
- i Cohorts 3 and 4: Blood samples will be collected 3 (within 15 minutes prior to the end of infusion using a separate line or immediately after the end of infusion using the same line and with proper flushing), 5, and 8 hours after the start of infusion.

Page 77 of 83

eGFR = estimated glomerular filtration rate; EOS = End of Study; EOT = End of Treatment; IV = intravenous; q8h = every 8 hours; SOC = standard of care

- a Screening will occur within 4 days prior to Treatment Day 1 or on Treatment Day 1.
- b EOT assessments will occur within 24 hours after administration of the last dose of study treatment or at early termination.
- c EOS visit will occur 28 (+ 7) days after administration of study treatment; on-site or via phone call.
- d Body weight measurement only, if clinically indicated and otherwise physical examinations should be symptom focused.
- e Clinical laboratory tests are mandatory at Screening, Day 1, one of the Days 2 to 4, one of the Days 5 to 14, and Posttreatment. If performed, as part of routine patient care, data from all additionally performed physical examinations and clinical laboratory will be collected during administration of study treatment until the last dose of study treatment.
- f Vital sign measurements will be taken 1 hour postdose, and prior to initiation of the next dose of study treatment. Data from vital sign measurements performed at other time points as part of routine patient care will be collected once daily during Screening and at least 3 times per day starting on Day 1 and continuing during administration of study treatment until the last dose of study treatment.
- g eGFR (based on Schwartz equation [10] if ≥ 3 months to < 1 year of age and modified Bedside Schwartz equation [11] if ≥ 1 to < 18 years of age) will be estimated at Screening and daily during treatment if clinically indicated. See [Section 7.5.3.1.2](#) for eGFR calculations and ranges.
- h Microbiologic samples should be obtained for all subjects before the first dose of study treatment; it's allowed to use samples obtained prior to informed consent, but directly related to the current infection. After initiation of study treatment, urine, blood or other samples, should be obtained where possible if clinically indicated. Identified isolates from subjects in the multiple-dose phase should be sent to the central laboratory.
- i Female subjects of childbearing potential only.
- j Multiple doses of cefiderocol administered as an IV infusion over 3 hours, q8h, beginning on Day 1 and continuing for an expected 5 to 14 days. Note: Shorter infusion times may be allowed in the multiple-dose phase if agreed on by the sponsor and in the best interest of the subject via the Request for Shortened Infusion Duration Form. In special circumstances, treatment beyond 14 days may be allowed following review and approval of individual cases by the Shionogi medical monitor via the Treatment Extension Form.
- k Cohort 2: Blood samples will be collected once at each time point: at 1, 3 (within 15 minutes prior to the end of infusion using a separate line or immediately after the end of infusion using the same line and with proper flushing), 3.5, 5, and 8 hours after the start of infusion for the single dose and Cohort 2 for the multiple dose phase during one of the dosing intervals from the 6th to the 12th dose of cefiderocol. Pharmacokinetic sampling schedule is shown in [Table 7-2](#).
- l Cohorts 3 and 4: Blood samples will be collected once at each time point at 3 (within 15 minutes prior to the end of infusion using a separate line or immediately after the end of infusion using the same line and with proper flushing), 5, and 8 hours after the start of infusion for the single dose and during one of the dosing intervals from the 6th to the 12th dose of cefiderocol during the multiple dose phase. Pharmacokinetic sampling schedule is shown in [Table 7-2](#).
- m Clinical outcome assessments will be performed at EOT, Posttreatment, and EOS if available; additional clinical outcome assessments may be performed as part of routine patient care.

-
- n Microbiological specimens may be collected as part of routine patient care and time points are not otherwise prespecified per protocol (EOT, Posttreatment Visit, and EOS, if applicable). In subjects where it is not possible to obtain a posttreatment culture and/or EOS culture, determination of presumed microbiological eradication maybe made based resolution of all presenting clinical sign and symptoms of the infection (clinical cure).

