- After administration of a single 1000-mg dose of [^{14}C]-cefiderocol infused over 1 hour, the majority of total radioactivity in plasma was accounted for intact drug. Additionally, 98.6% and 2.8% of the administered dose was excreted in urine and feces, respectively, with an overall recovery of total radioactivity (urine and feces combined) of 101.4% of the administered dose. More than 90% of the dose was excreted as unchanged cefiderocol in urine.
- After administration of a single 2000-mg dose of cefiderocol infused over 3 hours, the apparent terminal elimination half-life ($t_{1/2,z}$) of cefiderocol was 2.4 hours. A similar $t_{1/2,z}$ of 2.74 hours was estimated after administration of a single 2000-mg dose of cefiderocol infused over 1 hour (Study 1203R2111).
- Cefiderocol did not increase the C_{max} or AUC of furosemide (for OAT1 and OAT3) and metformin (for OCT1, OCT2, and MATE2-K). Cefiderocol increased the C_{max} and AUC of rosuvastatin (for OATP1B3) by 1.28-fold (90% CI, 1.12 to 1.46) and 1.21-fold (1.08 to 1.35), respectively (Study 1521R2115). These results suggest no clinically significant drug-drug interaction potential via these transporters.

- There was no clinically meaningful effect of age, sex, race, or body weight on the PK of cefiderocol based on a population PK analysis. No dose adjustment of cefiderocol based on demographic characteristics is considered to be necessary.
- A dedicated study to assess the potential effect of hepatic impairment on the PK of cefiderocol was not conducted. However, the need for a dose adjustment in subjects with hepatic impairment is not expected considering the primary route of elimination for cefiderocol is renal excretion.
- After administration of a single 1000-mg dose of cefiderocol infused over 1 hour, the geometric least squares mean ratios (GMRs) [renal impairment/normal renal function] and their 90% CIs for the AUC_{0-inf} of cefiderocol for subjects with mild, moderate, severe and end-stage renal disease (ESRD) requiring hemodialysis (HD) were 1.0 (0.8 to 1.3), 1.5 (1.2 to 1.9), 2.5 (2.0 to 3.3), and 4.1 (3.3 to 5.2), respectively. Dose adjustment of cefiderocol in subjects with renal impairment or augmented renal clearance is recommended.
- The 3- to 4-hour HD removed approximately 60% of cefiderocol dose. A supplemental dose immediately following HD is therefore recommended.

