In the single-dose phase, cefiderocol will be administered (in addition to SOC) at any time during the SOC treatment regimen. In the multiple-dose phase, cefiderocol will be administered on Day 1 (in addition to SOC), within 72 hours of the start of potentially effective treatment with SOC antibiotics for infection. Subjects will subsequently receive cefiderocol every 8 hours (q8h) for an expected 5 to 14 days; the total duration of cefiderocol administration will be determined by the investigator based on clinical assessment of each subject’s infection status. Each dose of cefiderocol will be administered IV over 3 hours. The infusion may be shortened if this is in the best interest of the subject and if approved by the sponsor via the Request for Shortened Infusion Duration Form. The single-dose phase will include only those subjects with normal renal function or mild renal impairment. The dose of cefiderocol for the single-dose phase will be determined based on body weight only; the maximum dose to be administered is not to exceed 2000 mg. The dose for the multiple-dose phase will be determined based on both body weight and renal function; the maximum dose to be administered is not to exceed 2000 mg. The SOC administered will be selected by the investigator based on the

suspected or confirmed pathogen(s) for the infection in accordance with local standards and can be modified at any time during the subject's participation in the study at the investigator's discretion. In the multiple-dose phase, if the subject's infection is confirmed to be Gram negative only before starting treatment, monotherapy with cefiderocol may be allowed.

End-of-treatment (EOT) assessments will occur within 24 hours after administration of cefiderocol (single-dose phase) or within 24 hours after administration of the last dose of study treatment (multiple-dose phase), or at early termination. A further clinical assessment will occur at a Posttreatment visit 7 (\pm 4) days after EOT (multiple-dose phase), which is analogous to a TOC and EOS time point, if microbiological samples are available. The EOS visit will occur 28 (+ 7) days after administration of cefiderocol in the single-dose phase or 28 (+ 7) days after administration of the last dose of study treatment in the multiple-dose phase; this visit may be performed on-site or via phone call. The study schematic including a schedule of assessments is provided in [Figure 3-1](#) and [Table 3-2](#).

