7.4 Pharmacokinetic Assessments

Pharmacokinetic studies in the paediatric population are generally conducted in patients with the disease to obtain data that better reflect clinical use of cefiderocol. The PK analyses in this study are mandatory and are being performed to determine PK parameters in different age groups to support cefiderocol dosing recommendations.

The total volume of blood withdrawn per subject in this study has been kept at a minimum by using micro tubes. The PK sampling schedule also allows for some flexibility in Cohorts 1 and 2, in terms of number of samples (3 to 5 samples, See [Table 7-2](#) for PK sampling times).

Several approaches will be used to minimize the amount of blood drawn and/or the number of venipunctures:

- Due to the use of a sensitive assay for cefiderocol, the volume of blood required per sample is 180 μ L, ie, 0.18 mL (0.36 mL in total for primary sample and back-up)
- To minimize discomfort of blood sampling, sites will be encouraged to use topical anesthesia to place IV catheters, to use indwelling catheters rather than repeated venipunctures for blood sampling, and to collect PK blood samples at the same time as routine, clinical blood samples are obtained, when possible
- The study uses PK and central laboratories experienced in handling small volumes of blood for PK analyses and for laboratory safety studies

At each PK sampling time point, up to 0.4 mL of blood (but no less than 180 μ L, ie, 0.18 mL) will be obtained, adding up to the maximum volumes shown in [Table 7-1](#):

Table 7-1 Total PK Blood Sample Volumes

Cohorts	Cohort 1	Cohort 2	Cohort 3	Cohort 4	Cohorts 1 and 2 Flexible Sampling	
Age	12 years to < 18 years	6 years to < 12 years	2 years to < 6 years	3 months to < 2 years	3-point design	4-point design
Number of samples	5 samples	5 samples	3 samples	3 samples	3 samples	4 samples
Total PK Blood volume	2.0 mL	2.0 mL	1.2 mL	1.2 mL	1.2 mL	1.6 mL

PK = pharmacokinetic

Cohorts 1 and 2: A total of 5 blood samples for determination of plasma cefiderocol concentrations will be collected from each subject as specified in [Table 7-2](#). In the multiple-dose phase, sampling will be done during one of the dosing intervals from the 6th to the 12th dose of cefiderocol. In the multiple-dose phase of the study in Cohort 2, if approved by the sponsor and is in the subject's best interests, it is acceptable adjust the sampling time points to a minimum of 3 or 4 samples (versus ideally 5 samples).

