Cohorts 3 and 4: A total of 3 blood samples for determination of plasma cefiderocol concentrations will be collected from each subject as specified in [Table 7-2](#) in the multiple-dose phase during one of the dosing intervals from the 6th to the 12th dose of cefiderocol (multiple-dose phase).

The option to use an indwelling catheter to facilitate blood sampling or application of a topical anesthetic cream prior to venipuncture is allowed.

Table 7-2 Blood Sampling Times after Start of Infusion

Cohort	Sampling Time Points (hours) After Start of Infusion				
	1	3*	3.5	5	8
Single-dose Phase					
Cohort 1	X	X	X	X	X
Cohort 2	X	X	X	X	X
Cohort 3		X		X	X
Cohort 4		X		X	X
Multiple-dose Phase					
Cohort 1	NA	NA	NA	NA	NA
Cohort 2	X	X	X	X	X
Cohort 3		X		X	X
Cohort 4		X		X	X

NA = not applicable

* Within 15 minutes prior to the end-of-infusion using a separate line or immediately after the end of infusion using the same line and with proper flushing.

If using a 3-point design, sampling times after the start of infusion are: 3, 5, and 8 hours. If using a 4-point design, sampling times after the start of infusion are: 3, 5, and 8 hours, and 1 or 3.5 hours.

For each blood sample collected, the actual sampling time will be recorded in the eCRF. In the event that shorter infusion times are approved by the sponsor, the PK sampling time points will need to be adjusted as described in the laboratory manual. See the laboratory manual for more details on PK sampling and management.

If the line for PK sampling is the same line used for drug administration, the line needs to be flushed with normal saline to avoid mixing with the infused drug solution.

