7.5.3 Clinical Laboratory Tests

This is a safety and PK study; therefore, clinical laboratory tests are mandatory and will be performed for all subjects in both the single- and multiple-dose phase. The laboratory tests listed in [Table 7-3](#) must be performed at Screening and within 24 hours of the cefiderocol infusion in the single-dose phase and at Screening, during cefiderocol treatment, and within 24 hours of the last dose of cefiderocol in the multiple-dose phase. Full details are listed in the Time and Events schedule in [Appendix 1](#). In the multiple-dose phase, in addition to prespecified time points, data from clinical laboratory tests performed at other time points as part of routine patient care will be collected as clinically indicated during administration of study treatment until the last dose of study treatment. If clinically indicated, and if part of routine patient care, eGFR should be checked daily to determine whether dose adjustments should be made. See [Section 7.5.3.1.2](#) for eGFR calculations and ranges.

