7.5.3.1.1 Clinical Laboratory Tests

Mandatory hematology, blood chemistry, and urinalysis parameters that will be assessed are presented in [Table 7-3](#).

Table 7-3 Mandatory Laboratory Tests

Category	Evaluation Parameters	
Hematology tests	Hematocrit Hemoglobin Platelet count	White blood cell count Differential white blood cell count
Blood chemistry tests	Aspartate aminotransferase Alanine aminotransferase Gamma glutamyltransferase Alkaline phosphatase Total bilirubin Total protein	Albumin Blood urea nitrogen Serum creatinine Blood glucose Sodium Potassium
Urinalysis (dipstick) ^a	Protein Glucose Bilirubin	Urobilinogen Occult blood Leukocyte esterase

a If the subject has a complicated urinary tract infection, urine microscopy and Gram stain should be performed if the local laboratory has capability (see [Section 7.5.3.2](#)). Dipstick is not required if microscopy is performed. Dipstick for leukocyte esterase is not required if urine microscopy shows white cells. If urine microscopy shows white cells and is cultured, no further characterization is needed.

The total volume to be drawn in the study may vary based on local/regional specific laboratory requirements and the clinical requirements for the individual subject. According to central laboratory, Eurofins, the average blood volume drawn for routine laboratory testing is 3.5 mL (minimum 1 mL, maximum 3.5 mL). As a general rule, total blood volume (including PK sampling) should not exceed 3% of the total blood volume over a period of 4 weeks, and should not exceed 1% at any single time. This recommendation leads to the allowable sample volumes, indicated in [Table 7-4](#) below:

Table 7-4 Maximum Allowable Research-related Blood Sample Volumes

Body weight (kg)	Circulating total blood volume (mL)	Maximum allowable sample volume over 4 weeks (mL) – 3% of total blood volume	Maximum allowable sample volume at single time (mL) – 1% of total blood volume
2.5 to 5	250 to 500	7.5 to 15	2.5 to 5
5 to 12	480 to 960	14.4 to 28.8	4.9 to 9.6
12 to 20	960 to 1600	28.8 to 48	9.6 to 16
20 to 30	1600 to 2400	48 to 72	16 to 24
30 to 70	2400 to 5600	72 to 168	24 to 56

Source: Ethical considerations for clinical trials on medicinal products conducted with minors [9].

The estimated total amount of blood per cohort is listed in [Table 7-5](#). The estimate is based on assumptions of 10 routine blood draws during the study. Fewer or more draws may be required based on clinical considerations.

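### In the multiple-dose phase, no mandatory creatinine is tied to the sampled PK interval, so the nearest required renal value can be about 3 days from the concentrations

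*Protocol*

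**What the plan says.** **Laboratory schedule.** Footnote e to the multiple-dose schedule in protocol Appendix 1 reads: "Clinical laboratory tests are mandatory at Screening, Day 1, one of the Days 2 to 4, one of the Days 5 to 14, and Posttreatment". Table 7-3 includes "Serum creatinine" in the mandatory panel, so each of these draws can yield an eGFR.

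**PK schedule.** Protocol Section 7.4 states that in the multiple-dose phase "sampling will be done during one of the dosing intervals from the 6th to the 12th dose of cefiderocol". Dosing is 8-hourly (Section 3.1: "Subjects will subsequently receive cefiderocol every 8 hours (q8h) for an expected 5 to 14 days"). For sparse sampling, "If using a 3-point design, sampling times after the start of infusion are: 3, 5, and 8 hours"; Table 7-2 sets those same times for Cohorts 3 and 4, and Cohort 2 ideally adds 1 and 3.5 hours.

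**Other renal checks.** Section 7.5.3: "If clinically indicated, and if part of routine patient care, eGFR should be checked daily". Appendix 1 footnote g says that eGFR "will be estimated at Screening and daily during treatment if clinically indicated". Footnote e also captures any further laboratory results from routine care. Section 7.4 encourages sites to combine PK and routine clinical draws where they can. Section 7.5.3 requires a draw within 24 hours of the last dose.

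**Analysis.** The population PK work is planned in a separate document (protocol Section 9.10; SAP Sections 2.1 and 9). SAP Section 11.3 lists eGFR. SAP Section 9.3 presents concentrations by cohort, phase, infusion time and nominal sampling time. Neither puts the two together.

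**The concern.** Multiple-dose PK is a primary objective, and Section 1.3 says that the PK data will be used to confirm dosing recommendations. Renal function is central to exposure for this drug. Section 1.2 reports: "More than 90% of the dose was excreted as unchanged cefiderocol in urine". It also gives adult AUC ratios of 1.5 in moderate and 2.5 in severe renal impairment. The multiple-dose phase enrols children with eGFR down to 15 mL/min/1.73 m² and doses them by renal function as well as weight.

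The single-dose phase is stricter on this point. It enrols only eGFR of 60 or above and doses by weight alone, yet Appendix 1 asks for a repeat predose eGFR when Screening is more than 24 hours old. The multiple-dose phase has no rule for how old the eGFR may be when PK is sampled.

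If the modellers want an eGFR that belongs to the sampled interval, the schedule does not guarantee one. With three samples per child in Cohorts 3 and 4, there is little other information on that child's clearance at that moment.

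**Working it through.** The documents state no gap between creatinine and PK, so there is no planned figure to reproduce. The check is timeline arithmetic.

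**Inputs.** Dosing every 8 hours (Section 3.1); sampled interval from dose 6 to dose 12 (Section 7.4); first Cohort 3 and 4 sample at 3 h and last at 8 h (Table 7-2); mandatory draws on Day 1, one of Days 2 to 4 and one of Days 5 to 14 (Appendix 1, footnote e).

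**When PK is sampled.** Dose k starts at 8(k − 1) hours.
- Dose 6: 8 × 5 = 40 h, samples at 43 to 48 h.
- Dose 12: 8 × 11 = 88 h, samples at 91 to 96 h.

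The last dose-12 sample is exactly 96 h after the first dose, so it always falls on Day 5, outside the Days 2 to 4 window.

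**Gap when each draw is at the clock time of the first dose.** Day D is then hour 24(D − 1). Gaps are in days from the 3 h sample to the nearest mandatory draw.

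| Days 2–4 draw on | PK at dose 6 | PK at dose 9 | PK at dose 12 | Largest gap, doses 6–12, if second draw is on Day 5 |
|---|---|---|---|---|
| Day 2 | 0.79 | 1.79 | 2.79 | 1.46 |
| Day 3 | 0.21 | 0.79 | 1.79 | 0.88 |
| Day 4 | 1.21 | 0.21 | 0.79 | 1.21 |

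The three middle columns put the second draw on Day 14.

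**The long case.** Day 2 draw at 24 h, PK at dose 12: 91 − 24 = 67 h and 96 − 24 = 72 h, which is 2.8 to 3.0 days. It holds only if the second draw is late:
- Day 6: 120 − 91 = 29 h.
- Day 7: 144 − 91 = 53 h.
- Day 8: 168 − 91 = 77 h, longer than 67 h, so the Day 2 value is again the nearest.

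The course must also run on. After 5 days of dosing (15 doses) the last dose starts at 112 h. Its draw is due by about 136 h, or 139 h counted from the end of a 3-hour infusion, so it lies at most 48 h from the 91 h sample.

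The outer limit is about 4.0 days: first dose just before midnight on Day 1, draw just after midnight, PK at dose 12, second draw late.

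**Illustration of typical gaps.** Assume that draw day, sampled dose and first-dose time are each chosen uniformly, laboratory draws are in the morning (05:00 to 09:00), and no routine-care creatinine is taken. The mean gap is then 1.1 days. It exceeds 1 day in 49% of cases, 2 days in 15% and 3 days in 2%. None of these assumptions is in the documents.

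**After the fix.** A draw with a PK sample makes the gap zero. A draw up to 24 h before the interval leaves at most 24 + 3 = 27 h to the first Cohort 3 or 4 sample. A draw up to 24 h after the interval leaves at most 24 h to the last. A Day 4 draw always remains possible for dose 12: that dose starts before 16:00 on Day 5 whatever the first-dose time, so at least the last 8 hours of Day 4 are within 24 h.

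**The case against.** **The harm sits in a plan not provided.** The documents do not say that eGFR is a covariate on clearance, which value would be used, or whether values are interpolated. A reader might infer that clearance will be modelled against a stale eGFR; the documents do not support that. This stands, and it limits the claim to what the schedule can supply. It does not remove the point, because no matching rule can recover a creatinine that was never drawn.

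**Other provisions narrow the gap.** Section 5.2 tells sites to follow renal function by routine practice and to change doses at once if it changes. Daily eGFR when indicated, capture of routine results and encouragement to combine draws all help, most of all in children whose renal function is moving. That also stands, but each provision is conditional.

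**Three days is a stacked worst case.** Agreed: it needs a Day 2 draw, PK at about dose 12, a second draw on Day 8 or later and no routine creatinine. A reader might take 3 days as typical; the illustration puts it at 2%.

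**No size of error follows.** A reader might infer a clearance error of 1.5-fold or more, or a child placed in the wrong renal band. A rise in eGFR from 45 to 70 would give 70/45 = 1.56 if clearance were proportional to eGFR, but both the rise and the proportionality are assumptions. The documents give no rate of change, and Section 4.3 excludes shock, vasopressors, multiorgan failure and dialysis. The data will also be pooled with other paediatric studies, which dilutes any effect.

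**The grid is missing.** Only the footnotes of the multiple-dose schedule could be read, so the absence of a rule is established for the available text only.

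**Conclusion.** The point holds as a scheduling gap. In the available text, no mandatory creatinine has to fall near the sampled PK interval. The nearest required value can be 2.8 to 3.0 days away in the aligned case and about 4.0 days at the extreme. The average is nearer 1 day under uniform scheduling without routine laboratory tests, and shorter where routine tests are done.

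The effect on the clearance estimates cannot be sized from these documents. It depends on the covariate model in the separate PK plan and on how fast renal function changes, and neither is given. This is not a contradiction or a calculation error, and it does not show that the PK objective fails. It is a cheap improvement that secures a contemporaneous renal value for a drug cleared mainly by the kidney.

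**What to change.** Amend footnote e of the multiple-dose schedule in Appendix 1. The mandatory Days 2 to 4 draw should be taken with one of the PK samples, or within 24 hours of the sampled PK interval. If PK falls on Day 5, take it on Day 4 inside that 24-hour limit. Leave the Days 5 to 14 draw unchanged: fixing it on Day 5 would leave a 14-day course with no mandatory safety draw until the end of treatment.

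In SAP Section 9.3.2, list the eGFR from that creatinine, with its date and time, beside the concentrations. Supply it to the population PK dataset, and state in the PK plan which eGFR is matched to which concentration.

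**Cost.** Wording in one footnote, listing columns for the eGFR and its time, and slightly less freedom in choosing the laboratory day. For a late first dose with PK at dose 12, the Day 4 draw may have to be in the afternoon or evening. No draw is added, and a shared venipuncture may save one. In Cohort 4, one PK sample of 0.4 mL plus the 1.0 mL routine draw assumed in Table 7-5 is 1.4 mL, below the lowest single-time limit of 2.5 mL in Table 7-4.
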